14.3. Return & Destruction

At the end of the trial, following the accountability of the returned/unused trial medication, and on the authorization of the ACC, trial medication will be destroyed on-site or returned to the depot for destruction. Once destroyed, a destruction certificate or record will be provided to the site.

15. MANAGING INTERRUPTION OF STUDY MATERIAL SUPPLY TO TRIAL CENTRES

Supply chain-related interruptions of study materials to trial centres may occur, especially in the context of a pandemic, in which case the following strategies should be adopted. If study BP machines are not available at the centre, participants should not be entered into run-in, but asked to return when BP machines are available, which may necessitate re-screening. If study treatment for any trial phase (Run-in/Period 1, Period 2 or Period 3 as in Figure 2) is not available at the centre or not certain to arrive in adequate time, the participant should delay the start of Run-in, which may necessitate rescreening. If a participant is on Run-in/Period 1 and Period 2 and/or 3 study treatment is not available or not certain to arrive in adequate time, then randomization should be delayed, which may necessitate extending or repeating run-in. If a participant is randomised and receiving Period 2 study treatment (see Figure 2, ie. could be receiving GMRx2-dose2, telmisartan 20mg/amlodipine 2.5mg, telmisartan 20mg/indapamide 1.25mg, or amlodipine 2.5mg/indapamide 1.25mg) but Period 3 study treatment is not available, then at the week 6 study visit participants should switch to open-label telmisartan 40mg and amlodipine 5mg. This open-label treatment should be continued until Period 3 study treatment is available at the centre, at which time a repeat clinic visit should be arranged and Period 3 treatment instituted. Home BP monitoring should be continued throughout and any additional tests instituted as required to ensure patient safety. There is no need to unblind. The final clinic visit of the randomised phase should be rescheduled for 6 weeks after the new start date of the Period 3 study treatment.

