8.4.2. Double-Blind Treatment Period

The 4-week single-blind active run-in will be followed by a 12-week double-blind period with randomization to one of the following four treatment groups:

Table 4: Treatment Groups in the Trial

Group	Intervention	N	Treatment
1	Triple - TAI (GMRx2)	600	telmisartan 20 mg/amlodipine 2.5 mg/indapamide 1.25 mg (GMRx2 dose 2). At Week 6 visit, forced up-titration to telmisartan 40 mg/amlodipine 5 mg/indapamide 2.5 mg (GMRx2 dose 3)
2	Dual - TA	300	telmisartan 20 mg/amlodipine 2.5 mg. At Week 6 visit, forced up-titration to telmisartan 40 mg/amlodipine 5 mg
3	Dual - TI	300	telmisartan 20 mg/indapamide 1.25 mg. At Week 6 visit, forced up-titration to telmisartan 40 mg/indapamide 2.5 mg
4	Dual - AI	300	amlodipine 2.5 mg/indapamide 1.25 mg. At Week 6 visit, forced up-titration to amlodipine 5 mg/indapamide 2.5 mg

T=telmisartan, A=amlodipine, I=indapamide

On the day of randomization visit (W0), all participants will be prescribed and dispensed trial medication to be taken between the randomization and Week 6 visit (period 2). On the day of the Week 6 visit, all participants will be prescribed and dispensed trial medication (the same initial treatment but at double dose) to be taken between Week 6 and Week 12 visit (period 3). **All participants will be up-titrated at Week 6**, unless the investigator believes there is a specific contraindication for a particular participant, such as symptomatic hypotension or is asymptomatic with very low home or clinical BP levels (i.e. SBP <100 mmHg). If a participant is asymptomatic but is judged to be not suitable for dose doubling, then they should be continued on existing trial medication at Week 6. For participants who are not up-titrated at Week 6, up-titration can occur after Week 6 and before Week 12, if appropriate. Week 12 visit date should remain unchanged.

Participants should take trial medication once daily in the morning either before or after breakfast immediately after taking home BP measurement.

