3.9.3 Protocol Deviations

Over a blind review meeting, before database lock, the different protocol deviations will be classified as minor or major and categorized by type (e.g. non-compliance to treatment, prohibited medication etc.) by the clinical team. The number of major protocol deviations will be summarized by type of deviations.

Major protocol deviation categories include, but are not limited to:

- Randomized even though ineligible.
- Received the wrong treatment.
- Non-adherence to study treatment (adherence < 80% or > 120%), for reasons known to be unrelated

to tolerability or efficacy e.g. participant moved overseas.

- Interruption to study treatment as a result of supply chain issues in which protocol-specified procedures were not followed.
- Insufficient valid home BP measurements for home blood pressure calculation at one or more of: baseline, Week 6 Follow-up Visit 1, Week 12 Follow-up Visit 2.
- Up-titration at Week 6 Follow-up Visit 1 was not performed for reasons other than those specified in the protocol.
- Other

A summary table will present the tabulations by major protocol deviation on the Safety Set. All protocol deviations (recorded or programmed) will be listed.

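### For an asymptomatic participant judged unsuitable for dose doubling at a site without Period 3 stock, Protocol Sections 15 and 8.4.2 give incompatible instructions on Week 6 treatment and on the final visit date

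*Protocol*

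**What the plan says.** Protocol Section 15 covers interrupted supply. Its relevant clause opens "If a participant is randomised and receiving Period 2 study treatment", names all four Period 2 regimens and, where Period 3 treatment is unavailable, continues "then at the week 6 study visit participants should switch to open-label telmisartan 40mg and amlodipine 5mg". It then says: "This open-label treatment should be continued until Period 3 study treatment is available at the centre". At that point a repeat clinic visit is arranged, Period 3 treatment starts, and the last clinic visit of the randomized phase is set six weeks after that start. The section's safety wording is "Home BP monitoring should be continued throughout and any additional tests instituted as required to ensure patient safety". It does not refer to Section 8.4.2 and does not mention investigator judgement about the switch.

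Protocol Section 8.4.2 gives the ordinary Week 6 rule. Everyone goes up in dose "unless the investigator believes there is a specific contraindication for a particular participant, such as symptomatic hypotension", or a very low blood pressure without symptoms (SBP below 100 mmHg). For the same visit it adds: "If a participant is asymptomatic but is judged to be not suitable for dose doubling, then they should be continued on existing trial medication". Later up-titration before Week 12 is allowed, and the Week 12 visit stays where it was.

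SAP Section 2.2.3 repeats the exemption for the Week 6 visit without mentioning supply gaps. SAP Section 2.3.3 lists temporary open-label therapy for supply shortages among the possible treatment changes, but does not say how it interacts with the exemption.

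**The concern.** Section 8.4.2 contains a safety exemption, and Section 15, read literally, overrides it. The participant concerned has been judged by the investigator to be unsuitable for a dose increase. If the Week 6 visit coincides with a Period 3 stock-out, one section keeps that participant on current medication and the other moves the participant to a regimen in which at least one component already being taken is doubled. Section 15 sees no need to unblind, so the site would not know which arm's dose change it was making.

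The visit date is also in dispute. SAP Section 3.10.2.1 takes the primary endpoint from home readings in the seven days before the second follow-up visit, so the date fixes which readings count.

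The situation is not hypothetical. SAP Section 3.5.3 says that supply interruptions moved follow-up visits for some participants, and SAP Appendix 2 reports supply-chain problems that interrupted the trial.

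**Working it through.** The plan states no figure on this point, so the check compares the texts, with some simple arithmetic.

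**1. The two rules side by side** (asymptomatic participant judged unsuitable for doubling, Week 6 visit, no Period 3 stock)

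| Item | Protocol 8.4.2 | Protocol 15 |
|---|---|---|
| Treatment at Week 6 | Existing Period 2 medication | Open-label telmisartan 40 mg and amlodipine 5 mg |
| Afterwards | May go up before Week 12 if appropriate | Period 3 treatment once stock arrives; no exception |
| Final visit | Week 12 date kept | Six weeks after Period 3 treatment starts |
| Strength of wording | should | should |
| Precedence over the other | None stated | None stated |

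**2. What the switch does in each arm.** Period 2 doses are from Protocol Table 4, and the open-label regimen is from Section 15. Doses are in mg, as T/A/I.

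| Arm | Period 2 | Planned Period 3 | Section 15 | Change from Period 2 |
|---|---|---|---|---|
| TAI | 20/2.5/1.25 | 40/5/2.5 | 40/5/0 | T ×2, A ×2, I dropped |
| TA | 20/2.5/0 | 40/5/0 | 40/5/0 | T ×2, A ×2 |
| TI | 20/0/1.25 | 40/0/2.5 | 40/5/0 | T ×2, A added, I dropped |
| AI | 0/2.5/1.25 | 0/5/2.5 | 40/5/0 | T added, A ×2, I dropped |

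In every arm at least one current component is doubled. Only in TA (planned 300/1500 = 20% of participants) does the switch equal the withheld doubling. In the other three arms doses move in both directions, and the documents give no net blood pressure effect.

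**3. Final visit date.** Suppose the Week 6 visit is on Day 42 and stock arrives *g* weeks later.

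- Section 8.4.2: Week 12, which is Day 84 with a window of ±7 days (Protocol Table 5), so no later than Day 91.
- Section 15: Week 6 + *g* + 6 = Week 12 + *g*.
- *g* = 1 gives Day 91, the edge of the window. *g* = 2 gives Day 98, which is 7 days beyond it. For any gap longer than one week, no single date satisfies both sections.
- If the participant is held and never starts Period 3 treatment, the Section 15 date has no starting point.

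**4. How many participants.** The documents give no count. SAP Appendix 2 says that more than 90% of 1500 were randomized, so more than 0.90 × 1500 = 1350; I assume 1400. I also assume that 5% to 20% reached Week 6 during a gap and that 1% to 5% of those met the exemption.

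- Low: 1400 × 0.05 × 0.01 = 0.7
- High: 1400 × 0.20 × 0.05 = 14

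Both percentages are assumptions, so the range shows only the order of size.

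**The case against.** The best reply is that the sections do different jobs: 8.4.2 decides who goes up, and Section 15 decides what to give when the planned kit is absent. A participant who is not going up needs no Period 3 stock at that visit. This is a sensible reading and may be what was meant. But Section 15 is triggered by Period 3 treatment being unavailable, covers anyone on Period 2 treatment, and does not defer to 8.4.2.

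Other provisions narrow the conflict. Section 8.7 lets the investigator stop or reduce medication for a condition or symptom likely to be related to it. Section 8.8 allows permanent discontinuation where safety is or will be compromised. Section 18.5 permits a deviation to prevent or eliminate immediate harm. These largely cover the participant with symptoms. None says which rule governs the participant with low blood pressure and no symptoms, so the conflict stands for that group.

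It is also fair to say that the switch removes indapamide in three arms, and that all participants took all three components at the lower doses during run-in. This rules out a claim of greater blood pressure lowering in every arm. It does not remove the contradiction.

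A reader might infer that SAP Section 3.9.3 turns a hold under 8.4.2 into a major deviation, because it lists "Interruption to study treatment as a result of supply chain issues in which protocol-specified procedures were not followed". The text does not support that. A held participant stays on blinded Period 2 medication, so study treatment is not interrupted. The same list counts a missed up-titration only when the reason is not one the protocol specifies, and SAP Section 3.10.1.1 words the intercurrent event in the same way. Classification is in any case left to a blind review before lock.

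**Conclusion.** The contradiction is real and narrow. It concerns an asymptomatic participant judged unsuitable for dose doubling whose Week 6 visit falls in a Period 3 stock-out. It affects both treatment and the final visit date, the latter once the gap exceeds about one week. In TA the switch is the withheld doubling itself; in the other arms the net effect on blood pressure is unknown.

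The number affected is unknown and probably small, and the effect on the primary estimate would be negligible. The point matters for participant safety and for clear instructions to sites.

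A reader might also infer that the conflict decides Per Protocol membership through the deviation list. It does not. Supply-related interruption is already an intercurrent event, so a switched participant leaves the Per Protocol Set on that ground, as would anyone switched for supply reasons. A held participant is not shown to have either an intercurrent event or a major deviation from the hold.

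This rests on the current text of Protocol 6.0 and SAP 2.0. Which clinical rule should prevail is not a question that this review answers.

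**What to change.** Reconcile Protocol Section 15 with Section 8.4.2 so that one stated rule governs participants judged unsuitable for up-titration when a supply gap coincides with Week 6. The rule should cover treatment at Week 6, what happens when stock returns, and the final visit date, including for someone who never starts Period 3 treatment. The clinical content is for the sponsor.

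Optionally, SAP Section 3.9.3 could confirm that a hold under the reconciled rule counts as a protocol-specified reason for not up-titrating. This would only make explicit what the text already implies.

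The cost is a sentence or two in Section 15, by amendment or site memo, and at most one in the SAP. The practical reach is limited. SAP Appendix 2 shows that stopping recruitment was recommended on 21 April 2023 and reports the final number randomized in the past tense, while Protocol 6.0 is dated 10 October 2023 and SAP 2.0 17 November 2023. The date of the last randomization is not given, so the change may reach few or no further Week 6 visits.

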16. MONITORING

16.1. Data & Safety Monitoring Board

An independent DSMB will monitor the trial data and advise the SC on the continuing safety of trial participants and those yet to be recruited to the trial, as well as the continuing validity and scientific merit of the trial.

16.2. Data Monitoring

In addition to pre-programmed edit checks in the eCRF, regular remote data monitoring will be conducted by the responsible CRO and designated monitors for confirmation of participant eligibility, identification of missing data, data consistency, and general data quality checks. Automated queries may be generated via programming in the eCRF and can also be manually generated by monitoring staff. On-site monitoring visits will also be conducted to review source documents and to resolve any issues at the site. Full details of monitoring activities will be described in the Trial Monitoring Plan. The investigator should allow the monitors, the persons responsible for the audit, the representatives of the sponsor, the IRB/IEC, and of the Regulatory Authorities to have direct access to source data/documents. The CRO will also undertake regular remote monitoring of data.

17. SAFETY

17.1. Safety Definitions

17.1.1. Adverse Event

An AE is any untoward medical occurrence in a participant administered a pharmaceutical investigational medicinal product and which does not necessarily have a causal relationship with this treatment. An AE can, therefore, be any unfavorable and unintended sign (including an abnormal laboratory finding), symptom, or disease temporally associated with the use of a medicinal (investigational) product, whether or not related to the medicinal (investigational) product. Only AEs that are defined as AESIs will be collected.

17.1.2. Adverse Event of Special Interest

The following AEs are considered AESIs and will be collected:

- Symptomatic hypotension: Dizziness or any other symptom or event possibly related to hypotension
- Abnormal laboratory findings of sodium, potassium, uric acid, glucose, lipids, creatinine or eGFR
- Headache
- Peripheral edema
- Any other symptom or laboratory abnormality that led to permanent discontinuation of trial medication.

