8.7. Down-Titration or Temporary Cessation of Randomized Trial Medication

If, during the randomized period a participant develops a condition or symptom likely to be related to the trial medication (e.g. possible hypotension) that is severe enough to warrant a change in trial medication, then the Investigator can choose to stop study medication temporarily or, if during Weeks 6 to 12, down-titrate to the

trial medication that the participant was receiving between Weeks 0 and 6. There is no need to unblind trial medication in this situation. Consideration should also be given to restarting scheduled medication subsequently, if benefits of restarting outweigh the risks as per the medical condition of the participant. If a participant discontinues medication at his/her own initiative, the reason should be investigated. If medically appropriate, consideration should be given to restarting study medication.

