9.2. Safety Outcomes

9.2.1. Primary

- Percentage of participants discontinued trial medication due to AE/SAE from randomization to Week 12.

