17.2.3. Reporting of AESIs & SAEs

At each trial scheduled visit and unscheduled visits during the trial, site staff will ask participants about the incidence of any AESIs or SAEs since the previous visit. Other AEs will not be recorded since these drugs are well-known and established with widespread use. Site staff may also become aware of the incidence of AEs during a phone call with participants. All SAEs that site staff becomes aware of from the time informed consent is obtained until 30 days after discontinuation of the trial medication must be recorded. The following information will be collected for each AESI and SAE: event name, date of onset, severity, a possible cause of the event, relationship to trial medication, action taken regarding the trial medication, treatment given to manage the event (if applicable), the outcome of event, and date of resolution (if applicable).

An increase in the severity of a previously reported AESI or SAE during the trial will be reported as a new AESI or SAE with higher severity. A decrease in the severity of a previously reported AESI or SAE during the trial, will not require changes to the reported severity. Worsening of a condition, recurrent episodes, and further complications if any are to be reported as a follow-up of the original event.

All SAEs will be reported by the site staff to the sponsor via the eCRF within 24-hours of first becoming aware

of the event. Additional information will be collected including, seriousness criteria, hospitalization date and discharge (if applicable), and procedures performed (if applicable).

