3.11.1.2 Adverse Event Summaries

For the summary of safety parameters, AEs will be classified according to the treatment period and treatment received as of the start date of the AE (Section 3.5.3). If an AE is ongoing at the time of randomization, it will be allocated to the Period 1 treatment. If a treatment ongoing at randomization worsens following randomization, the AE worsening will be allocated to the Period 2 treatment.

AESIs and SAEs will be classified according to the MedDRA (Medical Dictionary for Regulatory Activities) system (version 24.0, March 2021) and summarized by system organ class and preferred term.

Treatment periods for AE summary include: Period 1, Period 2, Period 3, Randomization Period, and Period 4. The total number of events and incidence of participants experiencing AESIs will be tabulated by treatment group and overall for the specified study periods.

For each period, any AESI or SAEs that emerges or worsens during the period of interest will be summarized:

- Adverse Events of Special Interest,
- Serious AE,
- Related AESIs defined as those judged by the investigator to be 'possibly', 'probably' or 'definitely' related
- Related SAEs defined as those judged by the investigator to be 'possibly', 'probably' or 'definitely' related,
- AE leading to trial medication discontinuation
- AE leading to trial discontinuation defined as a request by the participant to withdraw from future follow-up visits

AESIs of abnormality detected in laboratory assessments for Period 1 will only include those whose lab value for that parameter was in the normal range at baseline. Summaries of AESI and SAEs occurring during the Randomized Period will include risk differences with 95% CI, computed using the Newcombe hybrid score method (with continuity correction; https://pubmed.ncbi.nlm.nih.gov/21996567/), to evaluate GMRx2 against each dual control treatment group and overall. System organ classes and preferred terms with events occurring in at least 1% of the sample will be included.

In addition, the frequency and percentage of participants discontinuing treatment due to an AE will be reported with risk differences between treatment groups computed using the Newcombe hybrid score method (with continuity correction) to evaluate the primary safety endpoint among GMRx2 treatment participants compared to each dual control treatment group, and overall.

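### Dose changes made for intolerance are not counted by arm, and non-serious symptoms outside the AESI list that lead only to such changes are not collected

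*Protocol*

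**What the plan says.** **What is collected.** Protocol 17.1.1 limits non-serious events: "Only AEs that are defined as AESIs will be collected". Section 17.2.3 gives the reason: "Other AEs will not be recorded since these drugs are well-known and established with widespread use". Four AESI categories in 17.1.2 carry no condition about action taken. One is "Symptomatic hypotension: Dizziness or any other symptom or event possibly related to hypotension"; two more are headache and peripheral edema; the remaining one concerns laboratory results and is worded as "Abnormal laboratory findings of sodium, potassium, uric acid, glucose, lipids, creatinine or eGFR". The fifth category is the catch-all: "Any other symptom or laboratory abnormality that led to permanent discontinuation of trial medication". SAP 3.11.1.1 repeats the catch-all in terms of treatment withdrawal, and leaves headache out of its list. For each AESI or SAE, 17.2.3 also collects what was done with the trial medication.

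**What dose changes are allowed.** For a drug-related symptom severe enough to need a change, Protocol 8.7 lets the investigator "stop study medication temporarily or, if during Weeks 6 to 12, down-titrate". Section 8.4.2 lets the Week 6 doubling be withheld, for example for symptomatic hypotension or for very low pressure without symptoms. SAP 2.3.3 says add-on treatment, down-titration and temporary cessation are meant to keep people on trial medication.

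**What is analysed.** The primary safety outcome is "Percentage of participants discontinued trial medication due to AE/SAE from randomization to Week 12". SAP 3.11.1.2 plans risk differences for AESIs and SAEs against each dual. Its only action-based summaries are "AE leading to trial medication discontinuation" and discontinuation from the trial. SAP 3.6 (disposition) counts permanent discontinuation only.

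**The concern.** The secondary objective (Protocol 6.2) is the safety of GMRx2 against the duals at equivalent doses, and Protocol 7.1 says Dose 2 and Dose 3 are assessed in sequence. The randomized period after Week 6 is the first exposure to Dose 3. At that step the protocol offers alternatives to permanent discontinuation, while the primary safety outcome counts only permanent discontinuation.

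If three drugs lead to more dose reductions than two, the discontinuation rates could agree while fewer GMRx2 participants reached or kept the higher dose. A reader could then not tell how much of the Week 12 blood pressure effect, or of the Period 3 safety data, belongs to Dose 3. An imbalance is plausible on the protocol's own account: section 5.7 expects that effects of blood pressure lowering itself, such as dizziness and hypotension, may be increased with GMRx2.

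**Working it through.** The point rests on tracing a dose modification through the documents. The plan gives no rate or power figure for it. The arm sizes were set for efficacy, and that figure reproduces: with 600 v 300, SD 11 and a 3 mmHg difference, SE = 11 × √(1/600 + 1/300) = 0.778, and power = Φ(3/0.778 − 1.96) = 97.1%, against 97% stated.

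**Step 1: is the triggering symptom recorded?**
- Hypotension symptoms, listed laboratory findings, headache and edema: yes under the protocol, whatever the action (4 of 5 AESI categories).
- Any other non-serious symptom that leads to permanent discontinuation: yes, through the catch-all.
- Any other non-serious symptom that leads only to a temporary stop, down-titration or withheld up-titration: no.
- Withheld up-titration for very low pressure without symptoms: possibly no event at all, and action taken is collected only per AESI or SAE.

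**Step 2: is the dose modification itself counted by arm?**
- Protocol 9.2.1–9.2.3 and SAP 2.4.2: no primary, secondary or descriptive safety outcome covers it.
- SAP 3.6: no row.
- SAP 3.11.1.2: discontinuation of medication or trial only.
- SAP 3.9.1 (adherence): computed across both dose levels, so a return to the lower dose does not show. Gap days between logs get zero expected pills, so a logged stop does not lower the percentage.
- SAP 3.9.3 (deviations) and 3.10.1.1 (intercurrent events): non-up-titration counts only when the reason is not permitted by the protocol, so permitted tolerability cases fall in neither.
- SAP 3.5, Table 3-1: recognises a Period 3 state without up-titration, but no frequency is planned.

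Planned counts by arm found in the SAP text: none.

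**Step 3: illustration.** All rates are assumed. Arms are 600 (GMRx2) and 300 (one dual).
- Permanent discontinuation for an AE at 3% in both: difference 0, SE = √(0.03×0.97/600 + 0.03×0.97/300) = 1.21 points.
- Add AE-related dose modification in different participants, 5% v 2%. Any dose-limiting AE is then 8% v 5%: difference 3 points, SE = √(0.08×0.92/600 + 0.05×0.95/300) = 1.68 points, 95% interval 3 ± 1.96×1.68 = −0.3 to 6.3.
- If modification rates may be anywhere in 3–8% (GMRx2) and 1–3% (dual), the difference runs from 3 − 3 = 0 to 8 − 1 = 7 points.

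Precision of the proposed table, with two-sided 5% power (pooled variance under the null) and the Newcombe interval with continuity correction:

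| Assumed rates | Difference, 95% CI (points) | Power, 600 v 300 | Power, 540 v 270 |
|---|---|---|---|
| 4% v 2% | 2.0 (−0.9 to 4.3) | 33% | 30% |
| 6% v 3% | 3.0 (−0.3 to 5.8) | 49% | 45% |
| 8% v 3% | 5.0 (1.6 to 8.0) | 86% | 82% |

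The last column takes 90% of planned size, because SAP Appendix 2 says that over 90% was reached. At these rates the table supports estimates with intervals. It is not a basis for a formal test.

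**The case against.** The strongest reply is that the main dose-limiting symptoms are already covered. The protocol's own symptomatic examples for changing dose are hypotension symptoms, which are AESIs whatever the action. Symptomatic hypotension is a secondary safety outcome, AESIs are summarised for Period 3 separately, and over the randomized period they get risk differences against each dual. This stands. A reader might infer that only permanent discontinuation counts, or that tolerability is never compared between arms. The documents support neither: the condition sits on one of five AESI categories, and the listed symptoms are compared. What is not compared is the dose modification that follows them.

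Selective collection is also a stated choice, justified by long experience with the drugs, and everyone randomized had tolerated the triple at Dose 2 in run-in. That is a fair reason not to collect all adverse events. It is weaker for events severe enough to change the dose, and run-in says nothing about Dose 3.

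Two further limits stand. Part of the assumed 5% v 2% above would be listed AESIs, already captured as events, so the illustration does not measure what goes unrecorded. And the SAP revision history mentions table shells that are not in the text available, so the finding of no planned count rests on the SAP body.

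**Conclusion.** The point holds in two parts, both certain on the text of the plan. First, a collection gap: non-serious symptoms outside the list that lead only to a temporary stop, down-titration or withheld up-titration are not recorded as events. Second, a reporting gap: no count by arm of these modifications is planned, whatever the reason, and the adherence, deviation and intercurrent-event rules do not reveal them.

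The size cannot be known from the documents. The range of 0 to 7 points follows from assumed rates and includes no difference at all, so it would be wrong to infer that GMRx2 is less well tolerated than reported. The consequence is narrower: equal permanent discontinuation would not by itself show equal tolerability of the higher dose. This is a cheap improvement to reporting and does not affect the primary efficacy test.

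**What to change.** 1. **Main remedy, SAP 3.6 and 3.11.1.2.** Add a descriptive table by arm of withheld up-titration, down-titration, temporary cessation, and any of these, overall and AE-related. Give Newcombe risk differences of GMRx2 against each dual, as already planned for AESIs. Build it from the medication log and the action-taken field. The log is needed because changes made without an event have no action-taken entry. Since 8.4.2 allows later up-titration, separate never from delayed.
2. **Collection, Protocol 17.1.2 and SAP 3.11.1.1.** If collection is still open, extend the catch-all to symptoms or laboratory abnormalities leading to any of these dose actions, and note the date of change because capture before and after will differ. Recruitment had already been terminated when SAP 2.0 (17 November 2023) was written, so this may be too late. In that case, state in the report that unlisted symptoms leading only to dose modification were not captured.
3. **Reconcile the AESI lists.** The protocol includes headache and the SAP does not.

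The cost is one table, a few disposition rows and possibly some extra AESI forms. It assumes the final database holds the log and action-taken fields as described. The clinical rules in Protocol 8.4.2 and 8.7 stay as they are.
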